The SEC eCRF page records the end of study for every individual patient and should be completed for all patients enrolled in the Phase Ib part and those patients enrolled in the Phase II part who have progressed during study treatment, once the 30-day safety follow-up period is completed. For patients enrolled in the Phase II part who discontinue study treatment for any reason other than disease progression, the SEC eCRF should be completed upon progression or the initiation of subsequent anticancer therapies or death. Note: the survival FU assessments do continue beyond the SEC for all patients enrolled in the Phase II part.

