7.1.5.2 Disease progression follow-up period

Note: As of protocol amendment 10, no post-treatment disease progression follow-up will be performed.

Patients enrolled in the Phase II part of the study who discontinue study treatment for any reason other than disease progression will be followed up monthly via a phone call and will have CT/MRI scans every 8 weeks (± 7 days) as detailed in [Table 7-1](#) and [Section 7.2.1](#), until disease progression or the initiation of subsequent anticancer therapies, or death, or until all patients have completed SEC, or have been lost to follow-up or withdrew consent, whichever occurs first.

Patients who have been on the LGX818/MEK162 dual-combination or LGX818/MEK162/LEE011 triple-combination treatment for ≥ 24 months (Cycle 25 Day 1 onward) and then discontinue study treatment for any reason other than disease progression will be followed up by CT/MRI scans every 8-12 weeks (± 7 days) as detailed in [Table 7-1](#) and [Section 7.2.1](#), until disease progression, death, removal of consent to follow, the initiation of subsequent anticancer therapies or until End of Study (see [Section 4.3](#)), whichever occurs first.

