7.2 Assessment types

7.2.1 Efficacy assessments

Tumor response will be evaluated locally by the investigator according to the guideline based on RECIST version 1.1 (see [Appendix 1](#)). Each subject will be evaluated for all potential sites of tumor lesions at Screening/baseline, at the end of Cycle 1 (not applicable for patients enrolled

in the Phase II part of the study) and Cycle 2 and then every 8 weeks (2 cycles) thereafter during the study treatment until disease progression. Screening/baseline imaging assessments may be performed within 21 days of treatment start, except whole-body bone scans, if applicable, which can be performed within 6 weeks of treatment start. On-study tumor assessments have a ± 7 day window, except for the tumor assessment on C1D28 which must be performed between week 3 and 4 after starting the study drug combination. Patients who have been on the LGX818/MEK162 dual- or triple-combination treatment for ≥ 24 months (Cycle 25 Day 1 onward) will be evaluated for all potential sites of tumor lesions every 8-12 weeks (± 7 days) until disease progression.

There will be a tumor assessment at End of Treatment (± 3 days) if the patient discontinues for any reason other than disease progression and the last tumor assessment has been performed > 21 days prior to this day. Subjects included in the Phase II part of the study, who discontinue study treatment due to another reason than disease progression, should be followed up monthly via a phone call and undergo tumor assessments every 8 weeks (± 7 days) until disease progression or initiation of subsequent anti-neoplastic therapy, or death, whichever occurs first ([Section 7.1.5.2](#)). Patients who have been on either dual- or triple-combination treatment for ≥ 24 months (Cycle 25 Day 1 onward) and then discontinue study treatment for any reason other than disease progression will have CT/MRI scans every 8-12 weeks (± 7 days).

At Screening/baseline the following should be performed:

- A CT scan with intravenous (i.v.) contrast of chest, abdomen and pelvis is required for all patients.
- In subjects with a history of asymptomatic brain metastases, a brain MRI or CT scan must be performed.

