10.4.2.2 Phase II

Efficacy will be assessed using the local CT/MRI assessments evaluated under RECIST version 1.1, [Appendix 1](#). The Best Overall Response (BOR) for each patient and individual lesion measurements will be listed. The (BOR) is the best response recorded from the start of the treatment until disease progression. Based on patients' BOR during study, the Objective Response Rate (ORR) and the Disease control Rate (DCR) are then calculated.

The ORR is defined as the proportion of patients with a best overall response of Complete Response (CR) or Partial Response (PR). The DCR is defined as CR or PR or Stable Disease (SD).

Patients who withdrew prematurely due to progression of disease without having any post-dose tumor assessment will be classified as treatment failures. Similarly, patients who died due to their disease without having any post-dose tumor assessment will be classified as treatment failures.

Arm 1 dual combination: patients with metastatic BRAF V600 mutant mCRC

A Bayesian design will be used in order to estimate the true DCR. Inferential statements will be based on the uncertainty of this quantity. For a Bayesian design it is required to specify a prior distribution for the parameter of interest, in this case DCR.

For the current study, the prior clinical assumption for a MEK inhibitor in BRAF V600 mutant mCRC at pre-specified dose-levels will be used in order to derive a minimally informative unimodal Beta prior distribution that reflects the level of uncertainty around the DCR before starting the current trial. At completion of the study, this prior distribution will be updated with all the data available in this part of the study.

Once updated, the distribution summarizes the probability that the true DCR at the dose of the LGX818 and MEK162 combination used in the Phase II lies in the following categories:

- [0, 20%) unacceptable efficacy
- [20%, 30%) limited efficacy
- [30%, 40%) moderate efficacy
- [40%, 100%] clinically relevant efficacy

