10.5 Secondary objectives

10.5.1 Efficacy

Phase Ib. A secondary objective of the Phase Ib is to assess preliminary clinical anti-tumor activity of the combination in patients with BRAF V600-dependent advanced solid tumors. For all efficacy analyses the FAS will be used.

Anti-tumor activity will be assessed using the Investigator imaging assessments under RECIST version 1.1, [Appendix 1](#). The Best Overall Response (BOR) for each patient and individual lesion measurements will be listed. The (BOR) is the best response recorded from the start of the treatment until disease progression. ORR will be estimated for this patient population. TTR and DOR will be assessed if at least one responder is observed.

Phase II. Local imaging assessments will be used for all Phase II efficacy assessments of tumor activity. The FAS will be used.

Overall survival (OS) is defined as the time from start of treatment to date of death due to any cause. If a patient is not known to have died, survival will be censored at the date of last contact. Kaplan-Meier estimates with confidence intervals for median survival and survival probabilities for specific time points will be presented.

The secondary endpoint progression-free survival (PFS) will be analyzed using Kaplan-Meier estimates (including plots) with 95% confidence interval for median survival. If a patient has not had an event, he/she will be censored at the date of last adequate response assessment. PFS is defined as the number of days from the first day of treatment to the date of the first documented progression of disease or date of death, whichever occurs first. PFS will be summarized by arm.

Kaplan-Meier estimates based on all responders with 95% confidence intervals will be presented for the secondary endpoint duration of overall response (DOR). This analysis based on responders will be used as a descriptive analysis. DOR is the time between the date of first documented response (CR or PR) and the date of documented progression or censoring. Censoring will occur at the last adequate tumor assessment date at which continued response is documented.

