G	Deaths due to reason other than deterioration of 'Study indication'	(1) Date of last adequate assessment	Censored (only TTP and duration of response)

1=Definitions can be found in [Section 14.1.25](#).
2=After the last adequate tumor assessment. "Date of next scheduled assessment" is defined in Section 14.1.25
3=The rare exception to this is if the patient dies no later than the time of the second scheduled assessment as defined in the protocol in which case this is a PFS event at the date of death.

The primary analysis and the sensitivity analyses must be specified in the protocol. Clearly define if and why options (1) are not used for situations C, E and (if applicable) F.

Situations C (C1 and C2): Progression or death after one or more missing assessments: The primary analysis is usually using options (1) for situations C1 and C2, i.e.

- (C1) taking the actual progression or death date, in the case of only one missing assessment.
- (C2) censoring at the date of the last adequate assessment, in the case of two or more consecutive missing assessments.

In the case of two or missing assessments (situation C2), option (3) may be considered jointly with option (1) in situation C1 as sensitivity analysis. A variant of this sensitivity analysis consists of backdating the date of event to the next scheduled assessment as proposed with option (2) in situations C1 and C2.

Situation E: Treatment discontinuation due to 'Disease progression' without documented progression: By default, option (1) is used for situation E as patients without documented PD should be followed for progression after discontinuation of treatment. However, option (2) may be used as sensitivity analysis. If progression is claimed based on clinical deterioration instead of tumor assessment by e.g. CT-scan, option (2) may be used for indications with high early progression rate or difficulties to assess the tumor due to clinical deterioration.

Situation F: New cancer therapy given: the handling of this situation must be specified in detail in the protocol. However, option (1), i.e. censoring at last adequate assessment may be used as a default in this case.

Additional suggestions for sensitivity analyses

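### The PFS default ignores undocumented clinical progression because such patients are said to be followed, but the operative sections schedule no further scans for them, so secondary PFS and DOR lean upward

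*Protocol*

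**What the plan says.** **The analysis rule.** Section 10.5.1 defines a PFS event as documented progression or death. For everyone else: "If a patient has not had an event, he/she will be censored at the date of last adequate response assessment". Table 14-5 in Section 14.1.27 sets default event and censoring dates that apply unless the protocol or analysis plan chooses otherwise. Situation E is a stop recorded as disease progression on the investigator's clinical judgement, without documented PD. Default option (1) ignores it; option (2) makes it an event at the discontinuation date. The default is justified this way: "By default, option (1) is used for situation E as patients without documented PD should be followed for progression after discontinuation of treatment".

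**The follow-up rule.** Section 7.1.5.2 limits progression follow-up to Phase II patients "who discontinue study treatment for any reason other than disease progression will be followed up monthly via a phone call", with scans every 8 weeks. Section 7.2.1 repeats the limit for those "who discontinue study treatment due to another reason than disease progression, should be followed up monthly via a phone call". The end-of-treatment scan is planned only "if the patient discontinues for any reason other than disease progression and the last tumor assessment has been performed > 21 days prior" to that day. Section 4.1 restricts progression follow-up in the same way. Section 7.1.4 has the study evaluation completion page filled in for "those patients enrolled in the Phase II part who have progressed during study treatment, once the 30-day safety follow-up period is completed".

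**Text pointing the other way.** Section 14.1.30 says that patients who stop for reasons other than documented progression, death or loss to follow-up will be followed for progression. It then says that those stopped for undocumented progression are ideally still scanned. Section 7.2.1 permits an extra tumour assessment when symptoms suggest progression.

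**Amendment 10.** Post-treatment progression follow-up has ended for all patients (Section 7.1.5.2).

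**The concern.** The premise of the Situation E default fails for the patients it governs. Their recorded stop reason is disease progression, and that reason is what removes them from the end-of-treatment scan and from later scans. With no scan there is normally no documented PD, so the PFS rule treats them as not having progressed.

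The censoring is then triggered by the event being measured, so it is informative. The Kaplan-Meier PFS estimates in the Phase II arms would be too favourable. Duration of response is exposed too: Table 14-5 also governs it, and Section 10.5.1 ends DOR only at documented progression or censoring.

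**Working it through.** **1. Is there a plan figure to reproduce?** Not for PFS: the protocol gives no PFS target, event count or rate of clinical-only progression. The Section 10.8 operating characteristics do reproduce from exact binomial tails: 9 of 28 gives 9.0% and 85.2%, 7 of 41 gives 11.0% and 73.9%, and 16 of 40 gives 11.5% and 92.3%. They concern DCR and ORR, and no decision rule uses PFS.

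**2. What happens to a clinical-only progressor with no later scan, under option (1)?**
- Death after at most one missed assessment (B, C1): an event, dated at death and so later than the clinical progression.
- Death after two or more missed assessments (C2, option 1): censored at the last adequate assessment.
- No death recorded: censored at the last adequate assessment, or at Day 1 if there was none (Section 14.1.34).
- New anticancer therapy (F, option 1, the suggested default): censored at the last adequate assessment.

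**3. How large could the effect be?** Inputs from the protocol are 8-week scans with a ±7-day window (Section 7.2.1), a median PFS of 3.7 months for a BRAF inhibitor in mCRC (Section 1.1.3) and one of 5.3 months in melanoma (Section 1.1.2). The medians are illustrative only. Three inputs are assumed:
- exponential times
- a clinical-only share q of 5%, 10%, 20% or 30%
- a median time m from clinical progression to death of 1, 3 or 6 months

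This makes 24 settings of 400,000 simulated patients each. New therapy (Situation F) is not modelled.

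For progression time T and death time D, in weeks:
- last scan L = 8 × floor(T/8)
- missed scans = floor((D − L)/8)
- radiologic progressors: event at L + 8 ± 1
- clinical-only, option (1): event at D if missed ≤ 1, otherwise censored at L
- clinical-only, option (2): event at T
- clinical-only, scanning continued as Situation E assumes: event at L + 8 ± 1

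6-month PFS in selected settings:

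| Median | q | m | Option (1), no scans | Option (2) | Scanning continued |
|---|---|---|---|---|---|
| 3.7 | 5% | 1 | 35.8% | 35.3% | 35.5% |
| 3.7 | 20% | 3 | 39.1% | 34.9% | 35.5% |
| 3.7 | 30% | 6 | 42.9% | 34.8% | 35.7% |
| 5.3 | 5% | 1 | 49.0% | 48.6% | 48.7% |
| 5.3 | 20% | 3 | 52.1% | 47.9% | 48.5% |
| 5.3 | 30% | 6 | 55.8% | 47.7% | 48.6% |

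Against option (2) the overstatement runs from 0.4 points (49.0 − 48.6) to 8.1 points (55.8 − 47.7; also 42.9 − 34.8). Against continued scanning it runs from 0.3 points (35.8 − 35.5) to 7.2 points (55.8 − 48.6). It was upward in all 24 settings. About 15%, 53% and 73% of clinical-only progressors were censored for m = 1, 3 and 6 months; the rest were events dated at death.

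Medians are a poor gauge because they jump along the 8-week scan grid. In one short-survival setting (3.7 months, q = 20%, m = 1) the option (1) median, 5.20 months, was slightly below the 5.29 months with scanning continued.

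**4. How far does PFS conflict with the treatment-failure rule?** Section 10.4.2.2 says: "Patients who withdrew prematurely due to progression of disease without having any post-dose tumor assessment will be classified as treatment failures". It reaches only patients with no post-dose scan. Eight weeks is 56/30.44 = 1.84 months. With a 3.7-month median, the share progressing after the first scan is 0.5^(1.84/3.7) = 71%. On that assumption the mismatch could touch only the remaining 29% or so of clinical-only progressors.

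**The case against.** The strongest counter-argument is that the protocol does not remove imaging. Section 14.1.30 says such patients will be followed, Section 7.2.1 allows a scan on symptoms, Section 14.1.32 asks for careful review of undocumented progression stops, and the scan restrictions do not say whether they mean documented or clinical progression. This stands in part. It shows two instructions in conflict, not a ban on imaging. But the sections that sites work from, 7.1.5.2 and 7.2.1, sort patients by stop reason, and an optional scan is not a scheduled one.

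Second, the choice between options may be made in the analysis plan, which is not shown; Section 14.1.29 accepts that up to database lock. That is fair, so leaving the option open is not the fault. The fault is that the protocol justifies its default by a follow-up that its own schedule does not provide.

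Third, option (2) counts an investigator's unimaged claim as an event in an open-label trial. This stands, and argues against making option (2) the sole definition.

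Stronger readings that a reader might infer are not supported:
- That every such patient is censored. Early deaths remain events, and the fastest-deteriorating patients are the likeliest to die before two missed scans.
- That PFS generally contradicts ORR or DCR for the same patients. The Section 10.4.2.2 rule covers only patients never scanned after dosing.
- That the mCRC arm is hit hardest. The largest overstatement was 8.1 points at both medians tested.

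**Conclusion.** The conflict is real and lies inside the protocol: the reason given for the Situation E default is contradicted by Sections 4.1, 7.1.5.2 and 7.2.1. Patients stopped for undocumented clinical progression have no further scheduled imaging. They are either censored at the last adequate assessment or counted late at death, so PFS is biased upward. DOR shares the rule, but its bias was not quantified.

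The overstatement of 6-month PFS is about 0.3 to 8 percentage points. That range rests on assumed clinical-only shares of 5% to 30%, assumed survival after clinical progression, and exponential times. The documents supply none of these, so the actual size is unknown. PFS is a secondary, descriptive Kaplan-Meier summary, and the ORR and DCR decision rules do not depend on it. The point should be corrected, but it does not threaten the primary conclusions.

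**What to change.** 1. Reconcile Sections 4.1, 7.1.5.2 and 7.2.1 with Sections 14.1.27 and 14.1.30, and drop or correct the statement that these patients are followed for progression. Since Amendment 10 ended post-treatment follow-up, only the analysis can still be changed.
2. State in Section 10.5.1 or the RAP, before database lock, that PFS is reported under both Situation E options. Option (2), an event at the date of discontinuation for disease progression, should be at least a mandatory sensitivity analysis. Section 14.1.27 already allows it as one, and also where early progression is frequent or deterioration hampers tumour assessment. Apply the same pair to DOR.
3. Report how many patients per arm fall under Situation E, so that the size of the problem can be seen.

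Cost: one added PFS table (and its DOR counterpart) from the date and stop reason already on the end-of-treatment page. PFS under option (2) will be slightly shorter and will include investigator-claimed events without imaging. Presenting it beside option (1) avoids a late redefinition of the endpoint.

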14.1.28 Data handling and programming rules

The following section should be used as guidance for development of the protocol, data handling procedures or programming requirements (e.g. on incomplete dates).

14.1.29 Study/project specific decisions

For each study (or project) various issues need to be addressed and specified in the protocol or RAP documentation. Any deviations from protocol must be discussed and defined at the latest in the RAP documentation.

The proposed primary analysis and potential sensitivity analyses should be discussed and agreed with the health authorities and documented in the protocol (or at the latest in the RAP documentation before database lock).

14.1.30 Treatment and study completion CRFs

If study drug is discontinued, the **EOT Page** is to be completed with a visit date reflecting the date the discontinuation decision was made, and with the 'Last known date patient took study drug' and one of the following reasons:

- AE(s)
- Abnormal laboratory value(s)
- Abnormal test procedure results(s)
- Protocol violation
- Patient withdrew consent
- Lost to follow-up
- Administrative problems
- Death
- Disease progression
- Treatment duration completed as per protocol (optional, to be used if only a fixed number of cycles is given)

For reasons other than progression (and death) it should be checked if this was not in fact progression (especially reasons AEs, Abnormal laboratory value (s), Abnormal test procedure result and patient withdrew consent). Also it should be checked if patient withdrew consent because of safety issues, in which case reasons AEs, Abnormal laboratory value (s), Abnormal

test procedure result should be used. In such cases where the reason for discontinuation is AE, the AE CRF page must be consistent with the EOT reason provided

All patients who discontinued study drug will be followed for post a treatment evaluation until progression or until a new anticancer therapy is initiated. Patients who discontinued study drug for reasons other than documented progression, death or lost to follow-up will be followed for progression thereafter (patients who withdrew consent might not be followed with regular tumor assessments at the study site, but should ideally be followed until progression outside the study site). Ideally, all patients who discontinued study drug for progression without documented progression will still be followed with regular tumor assessments (e.g. in case of central radiology review). If patient withdraws consent, it must be clearly stated if patient is also withdrawing consent from post treatment evaluations and/or post treatment follow-up assessments. During that evaluation period, usually only tumor measurements (and/or response status) and survival data are collected. In some protocols, the subsequent anti-cancer therapies may also be recorded.

14.1.31 Study evaluation completion

At the end of the study evaluation period, the **study evaluation completion page** is filled out with the following options:

- Patient withdrew consent
- Lost to follow-up
- Administrative problems (when follow-up for progression has met protocol required events, e.g. follow-up stopped at certain number of events or certain time)
- Death
- New cancer therapy (optional, to be used when follow-up for progression is stopped in this case)
- Disease progression

Thereafter, patients will be followed for survival using the survival follow-up pages. If information on death becomes available for patients who were lost to follow-up or withdrew consent, this may also be entered in the database. The reason for death must be documented (and will be coded using MedDRA); it must be also stated if death was due to ‘Study indication’ or ‘Other’ reason.

In comparative studies with long follow-up period and therefore extended visit schedule, it may be useful to collect the survival status at a pre-specified cut-off within a limited timeframe for all patients with no documented death. In this case, this requires a contact to be made with the patient or with any reliable source of information on the patient’s status, but not requiring a specific visit to be scheduled.

Until the specified cut-off point has been reached, the goal is to collect tumor assessments until disease progression for all patients regardless of whether the patients are still receiving study drug. If patients are not followed for progression, e.g. in a Phase I or II study mainly evaluating safety, the evaluation is completed when study drug is completed (in this case only the first completion page is used).

